	5.1 Changes in the Conduct of the Study	
	5.2 Changes from the Analyses Planned in the Protocol	10
6	. Outcome Variables	
	6.1 Schedule of Assessments	11
	6.2 Objectives and Endpoints	12
7	. Statistical Methods	13
	7.1 Overview	13
	7.2 Data Cleaning	13
	7.3 Software	14
8	. Statistical Analysis	16
	8.1 Analysis Populations	16
	8.2 Handling missing data	16
	8.3 Measurements of treatment compliance	16
	8.4 Analysis of outcome parameters	16
٥	Peteronees	24

Abbreviations:

5-HT	Serotonin
ANOVA	Analysis of Variance
AVLT	Auditory Verbal Learning Task
BDI	Beck Depression Inventory
ВМІ	Body Mass Index
BOLD	Blood Oxygen Level Dependent
BRC	Biomedical Research Centre
CUREC	Central University Research Ethics Committee
DSM	Diagnostic and Statistical Manual of Mental Disorders
ECAT	Emotional Categorisation Task
EMEM	Emotional Recognition Task
EPQ	Eysenck Personality Questionnaire
EREC	Emotional Recall Task
ETB	Emotional Test Battery
FERT	Facial Expression Recognition Task
(f)MRI	(Functional) Magnetic Resonance Imaging
FSL	FMRIB Software Library
NART	National Adult Reading Test
OHBA	Oxford Centre for Human Brain Activity
PANAS	Positive and Negative Affective Schedule
PI	Principal Investigator
PILT	Probabilistic Instrumental Learning Task
PIS	Participant Information Sheet
ROI	Region of Interest
SAE	Serious Adverse Event
SCID-V	Structured Clinical Interview for DSM-V
SHAPS	Snaith-Hamilton Pleasure Scale
SPSS	Statistical Package for the Social Sciences
SSRI	Selective Serotonin Reuptake Inhibitor
STAI	Spielberger State-Trait Anxiety Inventory
VAS	Visual Analogue Scales

1. Synopsis

Study Title	The effect of seven day prucalopride administration on emotional processing in healthy volunteers
Brief Title	7 day prucalopride and emotional processing
Study Design	Double-blind placebo-controlled experimental medicine study.
Study Participants	Healthy participants
Number of Participants	50 (anticipated 25 per group)
Planned Study Period	24 months
Non-CTIMP Study	This study does not fit the MHRA definition of a clinical trial as we are not investigating the efficacy of prucalopride, but rather using it as a probe to understand the role of 5-HT4 receptors in emotional processing.
Intervention (s)	Prucalopride (Resolor) 1mg for 7 days versus placebo for 7 days

2. Introduction

2.1 Background

Depression is a common condition associated with a substantial health disability (Moussavi et al., 2007). Selective Serotonin Reuptake Inhibitors (SSRIs) are the most commonly prescribed antidepressants. However, for many patients these drugs have limited efficacy, a poor side-effect profile, and a slow onset of therapeutic action (Barbui & Hotopf, 2001). Pharmacologically, SSRIs produce an indirect activation of several serotonergic receptor subtypes. It is possible that more specifically targeting particular receptor subtypes may be a potentially useful approach to the development of antidepressant treatment that is more effective, better tolerated and faster acting. Recent evidence from animal studies suggests that agonists of the serotonin receptor subtype 4 (5-HT4) have rapid effects on depressionand anxiety-related behaviours. For example, administration of the 5- HT4 agonists RS67333 and prucalopride reduces immobility in the forced swim test (Lucas et al., 2007). Consistent with this, in a mouse corticosterone model of anxiety/depression, RS67333 produced rapid anxiolytic and antidepressant effects in a battery of tests, including the open field test, the elevated plus maze, the tail suspension test and the novelty suppressed feeding test (Mendez-David et al., 2014). Importantly, these effects were seen after only three days of treatment (Lucas et al., 2007), whereas they are usually only observed after chronic (2-3 week) treatment with conventional SSRIs. This raises the intriguing possibility that 5-HT4 agonism might lead to more rapid and sustained activation of 5-HT neurons than SSRIs, and therefore potentially more rapid reductions in symptoms of depression when used clinically.

Work in our group has revealed that short-term treatment with conventional antidepressants such as SSRIs produces positive biases in the processing of emotional information in healthy volunteers (Harmer, Goodwin, & Cowen, 2009). For example, seven days treatment with the SSRI citalopram decreased recognition of negative facial expressions and recall of negative vs positive stimuli (Harmer, Shelley, Cowen, & Goodwin, 2004). There is also evidence showing that antidepressants have early effects on neural activity, acting on limbic-cortical brain regions that are known to be dysregulated in depression (Ma, 2015). Indeed, a key study by Godlewska and colleagues from our group showed that 7-day treatment with citalopram reduced activity in the anterior cingulate, insula, amygdala and thalamus in response to fearful versus happy facial expressions. Importantly, depressed patients with the greatest reduction in neural activity across these areas went on to respond better to SSRI treatment (Godlewska, Browning, Norbury, Cowen, & Harmer, 2016)

Such effects might be important neuropsychological mechanisms in the mediation of clinical antidepressant action and may also be useful as biomarkers to screen for potential antidepressant activity of novel compounds. It is currently unknown whether activating 5-HT4 receptors has similar effects on emotional processing and neural activity. Such findings would be consistent with the animal studies and important further demonstration that 5-HT4 receptor agonism might be a potentially useful avenue for antidepressant drug development. A previous study in our group revealed acute prucalopride administration (1mg) in 40 healthy volunteers potentiated learning and memory, whereby significantly more words were remembered in a test of auditory verbal learning and memory, and fewer false alarms were

made in a delayed emotional recall task relative to placebo. A single dose of prucalopride did not, however, positively bias emotional processing.

This current study will therefore test the hypothesis that short-term, seven-day administration of prucalopride will have positive effects on emotional processing and neural activity. Prucalopride ("Resolor") is a 5-HT4 receptor agonist which is currently licensed for the symptomatic treatment of chronic constipation in adults. The standard dose given is 2 mg once daily with or without food, at any time of the day. Healthy volunteers will be randomised to receive seven days of prucalopride (1 mg i.e. half the standard dose) or placebo. On the seventh day of drug administration, they will complete a battery of computer-based tasks that measure emotional processing (tasks of attention, interpretation, and memory), non-emotional cognition, and undergo fMRI scanning during an emotional processing task and while resting (no active task engagement).

2.2 Responsibility for Statistical Analyses

[figure not shown]
The study researchers will be responsible for performing and reporting the analyses of the cognitive task data, MRI data, and demographics and psychometrics data based on this SAP.

2.3 Reproducibility of Statistical Analyses

A copy of all raw research data (questionnaire, task data, MRI scan data) will be kept on secure university computers so that all data processing and analyses on the data can be replicated.

4. Study Design

4.1 Summary of study design

This is a double-blind placebo-controlled parallel group experimental medicine study, which will be conducted at the University of Oxford, Department of Psychiatry. The site will recruit 50 healthy volunteers between the ages of 18 and 40. Study staff will identify potentially eligible participants from the general public, who will be made aware of the trial through advertisements on local information websites (e.g. Daily Info, Oxford University Gazette), newspapers, local magazines, on the radio and on the lab webpage, Facebook page and Twitter account, and in universities and other public places. Each participant will attend 3 study visits in total which will be conducted at the Department of Psychiatry. After having confirmed initial study eligibility by phone or email (Pre-Screening), participants will be invited to the department for the Screening Visit (2 hours). If this visit qualifies them as eligible, participants will be recruited into the study and will be invited for visits 2 and 3 on two consecutive days, no later than 1 month after the Screening Visit. Visit 2 will be the Research Visit 1 (~1.5 hours), and visit 3 will be the Research Visit 2 (~3 hours), where behavioural and neural parameters will be obtained. Self-report clinical symptom severity (mood, anxiety and side effects) will be measured on all visits, and before and after testing on visit 2 and visit 3.

4.2 Participants

50 healthy volunteers aged between 18 and 40 years

Inclusion Criteria

- Participant is willing and able to give informed consent for participation in the study
- Not currently taking any medications (except the contraceptive pill)
- · Male or female
- Aged 18-40 years
- Sufficiently fluent English to understand and complete the task
- Right handed
- Body Mass Index in the range of 18-30

Exclusion criteria

The participant may not enter the study if ANY of the following apply:

- Not fluent in English
- Any past or current Axis 1 DSM-V psychiatric disorder
- Current usage of psychoactive medication (except the contraceptive pill, the Depo-Provera injection or the progesterone implant)
- Current usage of any medication that will influence the MRI scan
- Current or past history of drug or alcohol dependency
- Currently pregnant or breastfeeding
- Study visits due to take place during the premenstrual week
- Not right handed
- Body Mass Index outside the range of 18-30
- History of cardiac, thyroid, or liver problems
- An autoimmune disorder
- · Current, or a history of, gastrointestinal disorder or irritable bowel syndrome

- Epilepsy
- Known lactate deficiency or any other problem absorbing lactose, galactose, or glucose
- Participation in a study which uses the same computer tasks as those used in the present study
- Participation in a study that involves the use of a medication within the last three months
- Smoker > 5 cigarettes per day
- Typically drinks > 6 caffeinated drinks per day
- Any contraindication to MRI scanning (e.g. metal objects in your body, pacemakers, significant claustrophobia)

4.3 Methods of assigning subjects to treatment groups

Eligible participants will be randomised to receive either seven-day prucalopride, or seven-day placebo administration. Randomisation will occur on the day of screening, or up to a maximum of four weeks after screening.

The randomization code will be drawn up by a researcher not involved in the study using an online randomization tool (www.sealedenvelope.com). Randomisation will be stratified for gender and blocked with a block size of 4.

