6. STUDY PROCEDURES

Baseline Assessments and Procedures

Individuals who are interested in participating in the study will be invited to attend a Screening Visit (maximum 2 hours). Demographic information will be collected:

Age (years, months), years in full-time education

Participants' eligibility to take part will be checked by recording the following:

- Weight, height, and BMI
- Number of cigarettes smoked per day, units of alcohol consumed per week, caffeinated drinks consumed per day
- Medical history (including family psychiatric history), details of current and past medication
- Current and prior use of drugs (to exclude for drug use in the three months prior to the study)
- Menstrual cycle (in order to avoid scheduling testing in the premenstrual week)
- SCID-V interview (Structured Clinical Interview for DSM-V) to probe for current or past psychiatric illness
- Urine pregnancy test (female participants only)
- MRI screening form to ensure no contraindication to MRI scanning
- Edinburgh Handedness Inventory (see APPENDIX G: STUDY QUESTIONNAIRES)

The following baseline assessments will be completed (APPENDIX G):

- Beck Depression Inventory (BDI)
- Eysenck Personality Questionnaire (EPQ)
- State and Trait Anxiety Inventory (STAI)
- Positive and Negative Affect Schedule (PANAS)
- Snaith-Hamilton Pleasure Scale (SHAPS) a measure of anhedonia
- National Adult Reading Test (NART) a measure of verbal intelligence
- Side effect questionnaire (to determine baseline of bodily symptoms/'side effects')
- Visual Analogue Scales (VAS) measuring subjective state

Participants will be asked to wait while their eligibility to take part is assessed by a medical doctor involved in the study (maximum 30 minutes). Any participant for whom additional information is required before an eligibility judgment can be made will be asked to return on a different day once this information has been obtained.

Eligible participants will be randomised, using an online randomisation tool, to receive either seven-day prucalopride, or seven-day placebo administration. Randomisation will occur on the day of screening, or up to a maximum of four weeks after screening. Randomisation after the screening visit will occur in the event that further information is needed before determining whether participants are eligible to take part (for example, if a participant needs to follow up with details of allergies, or previous studies they have taken part in). In this

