9. STATISTICS AND ANALYSIS

Do you have a statistical plan?	Yes X	No 🗌
If no, please justify.		
The IBM SPSS statistical software will be use to analyse all behavioural data.		
Demographic and baseline measures will be analysed using independent t-tests.		
Mood, anxiety, and side effect measures will be analysed using repeated measures analysis of variance (ANOVA).		
Behavioural task results will be analysed using between-groups analysis of variance (ANOVA).		
Any significant interactions will be followed up using simple main effect analyses. When assumptions of equality of variances are not fulfilled, the Greenhouse-Geisser procedure will be used to correct the degrees o freedom.		
Analysis of fMRI endpoints will be completed using the FSL software package.		
Number of Participants		
50 healthy volunteers (25 per group)		

Have you done a sample size calculation?	Yes 🖂	No 🗌
If yes, please give details below		
If no, please give details to indicate you have considered the implications the selected		
sample size will have on the study outcome		
We will be using the Emotion Test Battery, which is a well validated set of emotional proces sensitive to antidepressant effects. On the facial expression recognition task, one of the magnitudes is accuracy at recognising fearful facial expressions and a sample size of 25/group power to detect changes of the magnitude of those we have seen in a previous antidepres volunteer study [drug mean 10.64 (SD 9.77) vs. placebo mean 3.36 (SD 5.96) from Harmer Psych; ref 6].	nain outcom would give sant healthy	e e 0.9 y
Analysis of Outcome Measures		
Data analysis will take place at the University of Oxford, Department of Psychiatry and will be undertaken by the research team under the supervision of the Principal Investigator. All data will be analysed using a between-groups analysis of variance (ANOVA). Analysis of fMRI endpoints will be completed using the FSL software package.		·

Withdrawn participants' data will not be included in the analysis.

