4.5 Determination of Sample Size

We will be using the Emotional Test Battery, which is a well validated set of emotional processing tasks that are sensitive to antidepressant effects. On the facial expression recognition task (FERT), one of the main outcome variables is accuracy at recognising fearful facial expressions and this is the variable used for power calculations. Based on data acquired in (Harmer et al., 2004) comparing citalopram to placebo, if we aim for 0.9 power and a 0.05 false positive rate, a suggested total sample size is 38 (G*power) to ensure determination of group level differences at this variable if they exist. As 5HT₄ agonism is less well studied and the dose required of prucalopride for optimal agonism at the receptor is uncertain, we will aim for 25 individuals per group (total sample size of 50).

5. Changes in the Conduct of the Study or Planned Analyses

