8.4.1 Demographic data and psychometric data

To assess changes in subjective mood and anxiety before and after prucalopride/placebo administration, mixed model ANOVAs will be performed with time as a within-subjects factor and group as a between-subjects factor on STAI-S, PANAS, and VAS ratings. Post hoc analyses using independent samples t tests will follow up any significant interactions. A generalised linear model will be used to analyse side effects.

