8.4.2.1 Primary outcomes

Facial Expression Recognition Task (FERT):

As in previous work (Harmer et al., 2004, Harmer et al., 2009), data will be analysed using repeated measures analyses of variance (ANOVAs). Group (prucalopride or placebo) will be the between-subject factor, and emotion (6 levels) will be the within-subject factor.

Auditory Verbal Learning Task (AVLT):

The number of correctly recalled words on the following trials will be calculated: List A immediate recall trials 1-5. A repeated measures ANOVA will be used to examine if there is an effect of prucalopride administration on word recall (between subject factor: group; within-subject factors: List A acquisition trial). Independent samples t-tests will be conducted to test if there is a group difference in the number of words accurately recalled after a short or long delay (List A short and long delay trials respectively, and the number of intrusions (incorrect words not present in list) and repetitions (correct words recalled more than once in the same acquisition trial) across List A acquisition trials. Independent samples t-tests will also be used to compare List B immediate recall and delayed recognition performance (number of hits and false alarms) between the groups.

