8.4.3.3 Second level analysis

Data will be compared across all participants using a random effects "second/higher level analysis" to determine whether brain activity is significantly altered across participants or differs between groups of participants. For all fMRI tasks and the ASL data the following second level analyses will be run: a) whole brain analyses (i.e. looking at all voxels in the brain); b) small volume corrected analyses (i.e. image based analyses limited to the prespecified regions of interest listed section 8.4.3.5 below; c) a region of interest analysis (i.e. using the mean activity within the prespecified regions of interest listed in section 8.4.3.5 below. We will also consider adding grey matter and / or ASL maps and / or gender to the confounder variables as a confirmatory analysis.

For fMRI analyses the inputs are statistical maps of model fit derived from the first level analyses. For region of interest analyses (see section 8.4.3.5) summary estimates of activity (model beta parameter estimates) within predefined regions are extracted from the first level statistical maps and analysed as a dependant variable using standard statistical software (SPSS). For analyses looking at the change in activity induced by prucalopride the inputs will be differences in beta weight contrast images activity between placebo and prucalopride groups, calculated using a random effect, between subject analysis. Summary estimates derived from individual regions of interest (ROIs) will be treated as repeated measures.

For the ASL data the input to the second level analysis will be the first level maps. For resting state analyses, we will focus on the networks, which have been identified as showing significant differences in resting state connectivity between patients with depression and healthy controls: the default mode network; the salience network; the executive control

network; the affective network; the limbic network. We will also conduct exploratory analysis of all commonly identified resting state networks.

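### Randomisation is stratified for gender, but no specified behavioural or mood model includes it; if gender is prognostic, the between-group tests are mildly conservative

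*SAP*

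**What the plan says.** - **Allocation.** SAP 4.3: "Randomisation will be stratified for gender and blocked with a block size of 4". Protocol section 6 says only "Eligible participants will be randomised, using an online randomisation tool" and names no stratification factor. The target is 25 per arm (SAP 4.5: "we will aim for 25 individuals per group (total sample size of 50").
- **Primary behavioural models.** For the FERT, SAP 8.4.2.1 says: "Group (prucalopride or placebo) will be the between-subject factor, and emotion (6 levels) will be the within-subject factor". The AVLT ANOVA has group and acquisition trial. Short- and long-delay recall, intrusions, repetitions, List B and recognition are compared by independent-samples t tests.
- **Other behavioural models.** In SAP 8.4.2.2 and the table of planned comparisons, ECAT, EREC, EMEM, FDOT, PILT and OMT have group plus within-subject factors only. Significant interactions are followed up by t tests (SAP 8.4.2).
- **Mood and anxiety.** SAP 8.4.1: "mixed model ANOVAs will be performed with time as a within-subjects factor and group as a between-subjects factor on STAI-S, PANAS, and VAS ratings". The generalised linear model for side effects lists no terms.
- **Imaging.** SAP 8.4.3.3 says the team will consider adding grey matter or perfusion maps "and / or gender to the confounder variables as a confirmatory analysis".

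Neither document gives a reason for leaving gender out, or any figure for its relation to an outcome.

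**The concern.** Stratified blocking forces the two arms to be nearly alike in gender. If gender is related to the outcome, this removes one source of chance difference between the arms, so the group estimate really is more precise. An ordinary t test or ANOVA without gender does not know this. It keeps the gender variance in the residual and reports the precision of an unstratified trial. Tests then reject less often than their nominal level, intervals are too wide, and the precision bought by stratifying is not used. In a study of 50 people, this makes a null result a little harder to interpret. Leaving gender as something to consider in imaging also leaves a model choice open.

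**Working it through.** **Inputs.** From the documents: N = 50, 1:1 allocation, blocks of 4 within gender, nominal level 0.05 (taken as two-sided; the SAP does not say), and fear-accuracy figures from Protocol section 9: "drug mean 10.64 (SD 9.77) vs. placebo mean 3.36 (SD 5.96". Assumed: the share of outcome variance explained by gender (R²), 50% women, and d = 0.6 as an example of an effect below the planning value. No document gives these three.

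**1. The plan's own power.** Difference = 10.64 − 3.36 = 7.28. Pooled SD = √[(9.77² + 5.96²)/2] = 8.09. d = 7.28/8.09 = 0.90. Normal approximation with 25 per arm: 0.90 × √(25/2) = 3.18; Φ(3.18 − 1.96) = 0.889. The exact t test gives 0.876. The Protocol's stated 0.9 is therefore reproduced approximately, for a simple between-group comparison without gender.

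**2. Why the standard error is too large.** Set the outcome SD to 1. The unadjusted standard error is about √(4/50) = 0.283. With gender balanced, the true SD of the group difference is about 0.283 × √(1 − R²). At R² = 0.10 this is 0.268, so the reported standard error is about 5% too large (0.283/0.268 = 1.054). The 48-df critical value of 2.011 then acts as 2.011 × 1.054 = 2.12, a true two-sided level of about 0.039.

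**3. Simulation of the stated scheme** (gender-stratified blocks of 4, N = 50, 40,000 trials per setting; t test versus linear model with group and gender):

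| R² of gender | True size without gender | Power at d = 0.9, without → with | Power at d = 0.6, without → with |
|---|---|---|---|
| 0 | 0.050 | 0.875 → 0.875 | no gain |
| 0.05 | 0.045 | 0.881 → 0.890 | 0.550 → 0.570 |
| 0.10 | 0.040 | 0.886 → 0.905 | 0.551 → 0.592 |
| 0.20 | 0.029 | 0.898 → 0.935 | 0.553 → 0.642 |

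With gender in the model the size is 0.050 throughout. With 65% women the results are nearly the same.

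**4. Which planned tests this describes.** It describes comparisons of one value per person between arms:
- the AVLT t tests (delay, List B, intrusions, repetitions, recognition);
- PILT amounts won, lost and earned;
- post hoc t tests, including fear accuracy;
- group main effects;
- ROI means.

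**5. The critical interaction contrasts.** The planned-comparison table tests within-subject factor by group, for example FERT emotion by group. A gender effect that is the same for all six emotions is constant within a person and drops out of that test. A simulated six-level mixed ANOVA (N = 52 balanced, within-person correlation 0.3, 8,000 trials) gave:
- Gender effect equal across emotions, 10% of variance: power 0.826 without and 0.826 with gender; size 0.049 and 0.050.
- Gender by emotion effect, 10% of variance: size 0.020 without and 0.050 with; power 0.727 without and 0.826 with.

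The power levels depend on the drug effect assumed. Only the comparison within each line is informative.

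**6. Degrees of freedom at N = 50.** Simple comparison: 48 → 47. FERT interaction: 48 × 5 = 240 → 47 × 5 = 235. AVLT interaction: 48 × 4 = 192 → 47 × 4 = 188.

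**The case against.** A reader might infer that power is lost throughout, primary FERT contrast included. The documents do not support that. The loss exists only if gender is prognostic, and they give no figure. For the FERT emotion by group test, it needs gender to act differently by emotion, a further assumption without support in the text. A reader might also infer that positive findings are unsafe. They are not: the estimate is unbiased and the error is conservative.

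Other points on the plan's side:
- At the effect size used for planning, the loss is only 1 to 2 points for R² of 0.05 to 0.10, and d = 0.6 is not the plan's figure. This stands. However, SAP 4.5 goes from 38 to 50 participants because the receptor target is less studied and the optimal dose uncertain, so smaller effects are a realistic concern.
- The FERT model follows previous work, which helps comparability. This stands as a reason to show unadjusted means as well, but not as a reason for the test to ignore the design.
- Imaging already names gender as a possible confounder. This is only partial cover, because its inclusion is left to later choice.
- Adding gender as a main effect alone would not change the FERT interaction test, and the PILT ANOVA on the proportion of a group choosing correctly has no participant-level gender value. Both stand, and they shape the fix.

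**Conclusion.** The mismatch between design and analysis is plain in the text: gender is a stratification factor and is absent from every specified behavioural and mood model. The consequence is conditional and modest. For between-group tests with gender R² of 0.05 to 0.10, true size falls to about 0.045 to 0.040. Power falls by about 1 to 2 points at d = 0.9 and 2 to 4 points at d = 0.6. At R² = 0 there is no loss. For the critical within-factor by group contrasts, precision is lost only if gender acts differently by level. This is a worthwhile efficiency gain and a tightening of the specification, not a threat to validity. It rests on the assumed R², a two-sided 0.05 level and roughly the planned 50 participants. Since withdrawals and per-task exclusions can disturb the achieved balance, having gender in the model would also guard against imbalance in any one analysis.

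**What to change.** 1. In SAP 8.4.1 and 8.4.2, prespecify gender as a between-subject factor or covariate in every participant-level behavioural and mood analysis. In the repeated-measures models, include the gender by within-factor terms (gender by emotion for FERT, gender by trial for AVLT, and so on). Without these terms the critical contrasts gain nothing.
2. Replace the plain t tests, planned and post hoc, by a linear model with group and gender. List the terms of the side-effect model, gender included.
3. For the PILT, apply this to amounts won, lost and total and to the fitted learning parameters. Do not apply it to the group-level proportion as now defined.
4. In SAP 8.4.3.3, make gender a standing regressor in the second-level fMRI and ASL models, and permute within gender if randomise is used.
5. If gender is to stay out of any analysis, state why.

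Cost: one error degree of freedom in a simple comparison, 5 of 240 in the FERT interaction and 4 of 192 in the AVLT interaction, plus SAP wording. No new data are needed, because the stratum is known for every randomised participant.
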